9.4.3 Handling of missing values/censoring/discontinuations

Handling of missing daily pain score values within a week (within-week imputation)

The 24-hour average pain score is measured daily for seven consecutive days prior to randomization and then every day through the end of the study (See [Section 6.4.1](#)). At each visit, the weekly mean of the seven 24-hour average pain assessments will be calculated.

The weekly mean will be calculated based on the available assessments. If only one measurement is available, the mean will be based on that value.

Handling of missing weekly mean pain score values (weekly mean imputation)

The multiple imputation for the primary variable will be carried out on the weekly mean pain score.

The imputation procedure related to primary analysis is described in [Section 9.4.2](#) while the imputation procedure for the supplementary analyses is included in [Section 9.4.4](#). The details of these imputation rules will be specified in an Estimand Charter and in the statistical analysis plan prior to unblinding.

For all analyses, imputation of intermittent missing observations before treatment discontinuation will be carried out following a MAR mechanism for all treatment arms.

9.4.4 Supplementary Analyses

The supplementary analyses to the primary analysis will be performed on the FAS population.

The **first supplementary analysis** will be performed to quantify the treatment effect by considering the discontinuation due to any reason other than the administrative reasons (e.g. technical problems, study terminated by sponsor) and other than pregnancy as unfavorable outcomes (no difference to a placebo patient). The estimation method and handling of post randomization events will be same as for the primary analysis, except that missing data after discontinuation due to any reason other than administrative reason in the EMA401 arms will be multiply imputed according to a “jump-to-reference” assumption.

The **second supplementary analysis** will be performed to quantify the treatment effect of the investigational drug compared to placebo that would have been observed had all patients remained on their assigned treatment for 12 weeks. The handling of post randomization events

will be same as for the primary analysis, except that missing data after discontinuation for any reason will be imputed using the MAR assumption.

The **third supplementary analysis** will be performed to quantify the treatment effect of the investigational drug compared to placebo regardless of changes in the dose of concomitant medications for PHN and regardless of use of prohibited medications with potential confounding effect. Such treatment effect corresponds to a “treatment-policy/intention-to-treat” estimand.

9.4.5 Sensitivity analyses

The following sensitivity analyses will be performed corresponding to the primary and supplementary estimands.

The same ANCOVA model as for the primary estimation will be adopted. Post randomization events will be handled in the same way as in the primary and three supplementary analyses, respectively. Missing data after discontinuation will in a first step be imputed in the same way as for the primary and three supplementary analyses, respectively. For the EMA401 arms these imputed values will further be worsened in subsequent steps via the application of increasingly large penalties (tipping point analysis, [Permute 2015](#)).

9.5 Analysis of secondary variables

9.5.1 Efficacy variables

The following secondary efficacy variables will be evaluated:

1. To compare the efficacy of EMA401 over placebo in 24-hour average pain intensity score at Week 12, using an 11 point Numeric Rating Scale (NRS). This comparison will be done by testing the null hypothesis of superiority of at least one active dose of EMA401 over placebo while adjusting for multiplicity. The estimation of the treatment difference and missing data handling will be performed using the method of analysis mentioned for the primary analysis. Multiplicity adjustment for the pairwise comparisons will be performed using the closed MCP-Mod procedure. The closed MCP-Mod approach works by applying the maximum contrast test associated with standard MCP-Mod to all intersection hypotheses in a closed testing strategy. As known from standard MCP-Mod the maximum contrast test controls the type I error across multiple dose-response shapes, so it is a valid level alpha test for all intersection hypotheses, and can thus be applied in the context of the closed testing principle.
2. Responder analyses (based on at least a 30% or 50% improvement from baseline on NRS) will be performed in order to facilitate the interpretation of the results of the primary and supplementary analyses from a clinical relevance perspective. The responder status for each patient will be calculated based on the continuous weekly score measurements. For patients who prematurely discontinue study treatment, the responder status will be calculated after missing data are multiply imputed according to the approaches specified for the primary and three supplementary analyses. Further analyses will be performed by considering patients who discontinue study treatment due to specific discontinuation reasons as non-responders. Additionally, to study the effect of changes in doses of

concomitant medications for PHN, the use of prohibited medications and rescue medications on the responder criteria, a combined responder status of the patients will be calculated based on their continuous weekly score along with the use of the medications mentioned above. These analyses will be performed on the FAS population. The detail definition of the responder status and the corresponding secondary estimand and its supplementary estimands are defined in detail in an Estimand Charter.

From an analysis point of view, the resulting responder variables will be analyzed using a logistic regression model including all randomized patients and adjusting for the same covariates as the ANCOVA model for the primary analysis. Odds ratios will be estimated along with their 95% CIs.

The responder analyses will be performed for each visit, with the obvious modification in the definition for the week of interest.

3. Change from baseline to Week 12 in BPI-SF interference total score. This variable will be analyzed according to the same ANCOVA model as the one used for the primary variable.
4. Change from baseline to Week 12 in weekly mean of the 24-hour worst NRS pain score, using an 11-point Numeric Rating Scale (NRS). This variable will be analyzed according to the same ANCOVA model as the one used for the primary variable.
5. PGIC at Week 12. The proportional odds model with the same factors as the ANCOVA model for the primary variable will be used.
6. Change from baseline to Week 12 in NPSI. The total score NPSI (sum of 10 descriptor items) variable will be analyzed according to the same ANCOVA model as the one used for the primary variable. The temporal items will be summarized descriptively.
7. Change from baseline to Week 12 in ISI. This variable will be analyzed according to the same ANCOVA model as the one used for the primary variable.

Multiple imputation for the secondary variables will be carried out in a similar fashion as for the primary analysis of the NRS pain score. However, for PGIC no imputation will be performed because it is collected only at one post-baseline visit (Week 12 or Treatment Discontinuation visit). Thus the analysis for PGIC will be performed only on the observed cases. No multiplicity adjustment will be carried out for the secondary variables.

Summary statistics by treatment and visit will be provided for the secondary efficacy variables.

9.5.2 Safety variables

Safety analyses will be conducted using the safety (SAF) dataset. Patients will be grouped by the actual treatment received.

The assessment of safety will be primarily based on the frequency of adverse events (including death and non-fatal serious adverse events). Additional safety assessments include laboratory tests, physical examination (including examination of skin), vital sign measures and ECG evaluations. Clinically significant findings in these additional safety assessments will be reported as adverse events and analyzed as such. In addition all safety assessments will be summarized or listed as appropriate. The analyses of additional safety assessments will be defined in the statistical analysis plan.

9.5.2.1 Adverse events

Treatment-emergent adverse events (TEAEs) are defined as any adverse events that develops after initiation of study treatment or any event already present that worsens following exposure to the study treatment.

TEAEs will be summarized (number of cases as a percentage of number at risk) by treatment group. Number and percentage of patients with TEAE will be summarized by primary system organ class and preferred term for each treatment group during the double blind Treatment epoch and during the double-blind Treatment withdrawal epoch. Relationship to study medication will be classified as related (“probably related” and “possibly related”) and unrelated (“not related”). Severity will be classified as “mild”, “moderate” and “severe”. Serious TEAEs, drug related TEAEs, TEAEs by maximum severity and TEAEs leading to premature discontinuation from study drug will be presented in a similar format as adverse events. Additionally, a listing of patients with TEAE will be presented. Drug abuse-related adverse events (identified using a pre-specified search criterion) will be summarized during the double-blind Treatment epoch. To assess the potential for withdrawal effect, drug abuse-related adverse events will be summarized for the double-blind Treatment withdrawal epoch.

9.5.2.2 Potential risks and Expected events

Allergic dermatitis, elevation in hepatic enzymes and neutropenia are the potential risks related to EMA401. Dizziness, headache, nausea, pre syncope and upper respiratory tract infections are the expected events related to EMA401. The search criterion for each of these risks and events will be defined based on MedDRA. The incidence of potential risks and expected events will be summarized. The detailed analysis of potential risks and expected events will be specified in the statistical analysis plan.

9.5.2.3 Laboratory data

The summary of laboratory evaluations will be presented for 3 groups of laboratory tests: Hematology, Chemistry and Urinalysis.

Laboratory data will be summarized by presenting summary statistics of raw data and change from baseline values, and by presenting shift tables using clinically notable ranges (baseline to most extreme post-baseline value). Laboratory data, and specifically liver enzymes, will also be summarized by maximum change from baseline.

For liver enzymes, the number of subjects with newly occurring liver enzymes abnormalities will be summarized by treatment group. Plots related to analysis of laboratory data will be specified in the statistical analysis plan.

Urine pregnancy test results will also be summarized.

9.5.2.4 Vital signs

Vital sign measurements and their change from baseline will be summarized with descriptive statistics (mean, median, standard deviation, min, max) by visit. The number and percentage of subjects with clinically notable vital signs will be presented.

9.5.2.5 ECG evaluations

ECG intervals will be summarized by presenting summary statistics for change from baseline values. The (uncorrected) QT interval will be corrected according to the Bazett's and Fridericia's formulae. The incidence rates of clinically notable ECG abnormalities will be summarized.

9.5.2.7 Other safety evaluations

All clinically significant safety findings based on additional safety evaluations (e.g. ECG or physical examination including assessments of skin, lymph nodes, lung, etc.) must be reported as adverse events on the AE CRF. The statistical analysis of these findings will be done in the analysis of adverse events.

Other safety data will be summarized or listed as appropriate.

[figure not shown]
9.5.3 Resource utilization

Not applicable

9.5.4 Pharmacokinetics

EMA401 plasma concentration data will be listed by treatment, subject, and visit/sampling time point. A population PK model will be fitted to the data in order to investigate whether covariates (e.g. age, gender, weight, ethnicity, baseline laboratory values, concomitant medications, etc.) influence the PK of EMA401. The choice of covariates to be included in the final model will be guided by exploratory plots of random effects (inter-individual variability parameters) against covariates. Those that are judged to show evidence of a relationship with the random effects will be tested for entry into the model, using the likelihood-ratio test with $p < 0.05$. The final covariate model will be derived using a rigorous and acceptable model building procedure.

Pregabalin and gabapentin plasma concentration data will be listed and summarized by visit and EMA401 treatment group. Descriptive comparisons between the baseline visit assessments and the post-baseline visit assessments will be made.

9.5.6 Biomarkers

[figure not shown]
[figure not shown]
Not applicable.

9.5.7 PK/PD

[figure not shown]
[figure not shown]
Evaluation of effect of EMA401 exposure on efficacy variables (e.g. change from baseline of pain score), via the development of a continuous descriptive Pharmacokinetics/ Pharmacodynamics (PK/PD) will be done. All population PK/PD analyses and simulations will be carried out using a non-linear mixed-effects modelling approach.

9.6 Analysis of exploratory variables

The following exploratory analysis will be performed:

4. The proportion of patients who need rescue medication (at each visit and at least once during the study) will be evaluated. The corresponding binary variables will be derived and analyzed based on a logistic regression model with the same factors as the ANCOVA model for the primary analysis.
5. The time to first rescue medication intake will be compared between each dose of EMA401 and placebo via a Cox proportional hazard regression model with the same set of covariates used for the primary analysis. The corresponding hazard ratio with the 95% confidence interval will be reported. The Kaplan-Meier estimates of the proportion of patients with rescue medication intake, along with the associated 95% confidence intervals using the Greenwood's formula will be provided.

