5.5.6 Rescue medication

Patients will be allowed to take acetaminophen/paracetamol up to a maximum of 3 g daily (divided into 3 or 4 times/day) for unacceptable pain due to any reason during the study. Acetaminophen/paracetamol will not be provided by Novartis.

[figure not shown]
The patients will be instructed to complete the pain scores in eDiary before intake of acetaminophen/paracetamol when taken due to unacceptable pain due to PHN.

The intake of acetaminophen/paracetamol in eDiary is to be recorded by the patient only when taken for unacceptable pain due to PHN.

The intake of acetaminophen/paracetamol if taken, for unacceptable pain due to any other reason, should be recorded in the eCRF as "other rescue medication" by the designated investigator staff.

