Nonsteroidal Anti-inflammatory Drugs (NSAIDs) or any other over-the-counter pain medications	2 weeks prior to Randomization and after Randomization	None

Medication	Prohibition period	Action taken for study treatment
Any non-drug therapies that could modulate the perception of pain either directly or indirectly (i.e. transcutaneous electrical nerve simulation (TENS) or surgery)	2 weeks prior to Randomization and after Randomization	Discontinue study treatment
Other medications that may have potential drug-drug interactions* (e.g. felodipine, eplerenone, nisoldipine, ticagrelor, tacrolimus, avasimibe, rifampin, cyclosporine, gemfibrozil, clarithromycin, St. John's Wort; oral, injected or implanted hormonal methods of contraception) , Antiviral medications (e.g. valacyclovir, acyclovir, amantadine, anti-HIV), Antifungals (e.g Azoles)	2 weeks prior to Randomization and after Randomization	None
Prohibited after Randomization and throughout study		
Any change to a different standard of care medication from baseline (e.g. switch from pregabalin to gabapentin) will be treated as prohibited medication	After randomization	Discontinue study treatment

(*Prohibited due to potential Drug-Drug Interactions (DDIs), please refer to Investigator Brochure Ed 11, Section 5.1.5.2 for details)

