
Table 6-1 Assessment schedule

Epoch	Screening	Treatment									Treatment withdrawal
		101	102	103	104	105	106	107	199	TD visit	
Visit	1	101	102	103	104	105	106	107	199		201
Week	-5 to -1	0 (BL)	1	2	4	6	8	10	12	TD visit	13
Day	-35 to -7	1	8	15	29	43	57	71	85		92
Informed consent	X										
Inclusion/Exclusion criteria	X										
Demography	X										
Disease & Medical History	X										
Smoking, Alcohol, Liver History	X										
Surgical and medical procedures/Concomitant Medications/Rescue Medications	X	X	X	X	X	X	X	X	X	X	X
Complete Physical exam	S	S							S	S	S
Brief Physical exam			S	S	S	S	S	S			
Vital signs	X	X	X	X	X	X	X	X	X	X	X
Height	X										
Weight	X	X							X	X	
Urine drug screen	X				X						
Serum pregnancy test ^{1,2}		X							X	X	
Urine pregnancy test	X				X		X				X
Hematology/Blood chemistry	X	X	X	X	X	X	X	X	X	X	X
Urinalysis ³	X	X			X		X		X	X	X
12-lead ECG ^{5,6}	X	X			X		X		X	X	X
Contact IRT	X	X	X	X	X	X	X	X	X	X	X
Dispense study medication		S	S	S	S	S	S	S	S ⁷		

Epoch	Screening	Treatment									Treatment withdrawal
Visit	1	101	102	103	104	105	106	107	199	TD visit	201
Week	-5 to -1	0 (BL)	1	2	4	6	8	10	12		13
Day	-35 to -7	1	8	15	29	43	57	71	85		92
Dosage Administration Record		X	X	X	X	X	X	X	X		X
Treatment Compliance			S	S	S	S	S	S	S		S
Adverse Events/SAEs	X	X	X	X	X	X	X	X	X	X	X
Dispense ePRO eDiary device	S										
Complete pain diary daily (NRS)	X	X	X	X	X	X	X	X	X	X	X
Record VRS pain intensity		X									
Check electronic tablet for eligibility		S									
BPI-SF		X			X		X		X	X	
PGIC									X	X	
NPSI		X			X		X		X	X	X
ISI		X							X	X	
Pharmacokinetics		X ¹⁰					X ^{9,10}		X ^{9,10}		
Screening disposition	X										
Treatment epoch disposition									X	X	
Treatment withdrawal epoch disposition											X
TD = Study Treatment Discontinuation visit X = assessment to be recorded on clinical data base; S = assessment to be recorded on source documentation only ¹ Collected as part of the blood chemistry. ² Required for all pre-menopausal women who are not surgically sterile. ³ Urine dipstick to be performed at the site. If abnormalities are present, urine sample should be sent to the central laboratory for microscopy analysis.											

Epoch	Screening	Treatment									Treatment withdrawal
Visit	1	101	102	103	104	105	106	107	199		201
Week	-5 to -1	0 (BL)	1	2	4	6	8	10	12	TD visit	13
Day	-35 to -7	1	8	15	29	43	57	71	85		92

⁵Triplicate ECG and PK sample should also be collected if abnormal ECG result (QTcF>500 ms).

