9.4.2 Statistical model, hypothesis, and method of analysis

The aim is to estimate the treatment effect of the investigational drug (EMA401) compared to placebo, for the target population on the primary pain parameter. The definition and the justification of the corresponding primary estimand, as well as the definition of the supplementary and secondary estimands are detailed in an Estimand Charter.

The primary estimation method is based on an Analysis of Covariance (ANCOVA) model including region (e.g. US, EU), treatment, sex, use of concomitant pain medication for PHN (yes/no) as factors and baseline (mean pain intensity) score and age as covariates. The analysis will account for different post-randomization events as follows:

- **Changes in doses of concomitant medication for PHN:** Efficacy observations collected during the period of changes in doses of concomitant medication for PHN (compared to

baseline) and the 2-days thereafter will be excluded, since they are considered affected by the concomitant medication dose change. The resulting missing data after this step will be multiply imputed using the Missing at random (MAR) assumption.

- **Intake of rescue medication:** Efficacy data collected during intake of rescue medication will be used for analysis.
- **Intake of prohibited medications with potential confounding effect prior to study treatment discontinuation:** The prohibited medications with a potential confounding effect are defined as those listed in [Table 5-2](#) requiring study treatment discontinuation. Efficacy observations collected during the intake period of such prohibited medications and the 7-days thereafter will be excluded, since they are considered affected by the prohibited medication intake. The resulting missing data after this step will be multiply imputed using the MAR assumption.

The design feature of retrieved drop-outs, considered in order to minimize the occurrence of missing data on primary pain parameter, is exploited for the statistical analysis as follows:

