2.4.2.1 Rescue medication

The number and percentage of patients who received rescue medication (Acetaminophen/Paracetamol as reported on the diary page) will also be summarized by treatment and by visit during the double blind and treatment withdrawal period separately. Visit mapping will be done according to the visit window strategy document. The dose received will be listed.

Analysis of time to first use of rescue medication will be performed using Kaplan-Meier curves. Number of patients with at least one intake will also be summarized.

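### The exploratory model for need of rescue medication leaves out rescue use before randomization, a small and cheaply avoided loss of efficiency, not a bias

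*Protocol*

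**What the plan says.** The primary ANCOVA in protocol section 9.4.2 is described as "including region (e.g. US, EU), treatment, sex, use of concomitant pain medication for PHN (yes/no) as factors and baseline (mean pain intensity) score and age"; SAP section 5.5.1.1 lists the same terms. For the proportion of patients who need rescue, at each visit and at least once during the study, protocol section 9.6 (item 4) and SAP section 2.13 (item 1) reuse that list: the variables are "analyzed based on a logistic regression model with the same factors as the ANCOVA model for the primary analysis". Neither document adds a term for rescue use before randomization.

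For time to first intake, protocol section 9.6 (item 5) plans a comparison "via a Cox proportional hazard regression model with the same set of covariates used for the primary analysis". The current SAP does not carry this model. Section 2.4.2.1 says "Analysis of time to first use of rescue medication will be performed using Kaplan-Meier curves", and section 2.13 (item 2) gives Kaplan-Meier estimates with confidence intervals. SAP section 4 does not list the removal of the Cox model.

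On data collection, the Table 6-1 row "Surgical and medical procedures/Concomitant Medications/Rescue Medications" is marked at Visit 1 and at Visit 101, and the eDiary is handed out at screening. Protocol section 5.5.6 allows acetaminophen/paracetamol "for unacceptable pain due to any reason during the study" and adds: "The intake of acetaminophen/paracetamol in eDiary is to be recorded by the patient only when taken for unacceptable pain due to PHN". Intake for other pain goes to the eCRF. Table 5-2 prohibits "Nonsteroidal Anti-inflammatory Drugs (NSAIDs) or any other over-the-counter pain medications" from 2 weeks before randomization and afterwards, and does not say how the rescue drug stands to that row.

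**The concern.** The pain ANCOVA adjusts the outcome for its own baseline value. When its covariate list is carried over to a different outcome, baseline pain stays and the new outcome has no baseline term. A patient who already takes rescue regularly is likely to count as a user at least once during the study in any arm, so part of the variation in the outcome may be explained by something known before randomization.

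What is at stake is precision on a named exploratory objective. It matters a little more here because the trial stopped at 129 of 360 planned patients (SAP, Amendment 1), which is 129 / 3 = 43 per arm over the three arms that were opened.

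**Working it through.** **The plan's own figure.** The only power stated is at least 77% for the primary dose-response test (protocol 9.8). It reproduces: with 90 per arm, SD 2.6, maximum effect 1.0 and one-sided 0.025, the lowest power over the five candidate shapes is 77.0% on the b.i.d. dose scale. It has no bearing on the rescue model, for which no power is stated.

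**Inputs.** From the documents: 90 per arm planned and about 43 per arm actual. Assumed, because the documents are silent: one dose against placebo, Wald test at two-sided 5%, conditional treatment odds ratio 0.5, rescue proportion on placebo 30-70%, baseline use 30-50%, and an odds ratio of 2, 5 or 10 linking baseline use to later use.

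**Formulas.** For baseline users and non-users separately, let v0 and v1 be n·p·(1 − p) in the placebo and active arms.
- With the covariate: information on the log odds ratio = sum over the two strata of v0·v1/(v0 + v1); SE = 1/√information.
- Without it: SE² = 1/[n·P0·(1 − P0)] + 1/[n·P1·(1 − P1)], where P0 and P1 are the overall proportions.
- Power = Φ(|log OR|/SE − 1.96).

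**Worked example at the unfavourable end** (placebo 50%, baseline use 50%, predictor OR 10, n = 90).
- Placebo: odds in non-users 1/√10 = 0.316, so 0.240; in users √10 = 3.162, so 0.760; average P0 = 0.500.
- Active: the odds are halved to 0.158 and 1.581, so 0.1365 and 0.613; average P1 = 0.375.
- Overall OR = (0.3746/0.6254)/1 = 0.599, and 1 − ln(0.599)/ln(0.5) = 26% shrinkage on the log scale.
- Without the covariate: SE = √(1/22.5 + 1/21.09) = 0.303; z = 0.513/0.303 = 1.69; power 39.4%.
- With it (45 per arm in each stratum): information = 8.215·5.304/13.519 + 8.215·10.68/18.89 = 3.22 + 4.64 = 7.87; SE = 0.357; z = 0.693/0.357 = 1.94; power 49.4%. The loss is 10 points.
- At n = 43 the same steps give 21.5% and 26.9%, a loss of 5.4 points.

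**Full range over the assumed placebo rates and baseline prevalences:**

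| Predictor OR | OR without the term (0.50 with it) | Shrinkage of log OR | Power loss, n = 90 | Power loss, n = 43 |
|---|---|---|---|---|
| 2 | 0.507-0.510 | 2-3% | 0.7-1.1 points | 0.4-0.7 points |
| 5 | 0.53-0.55 | 9-14% | 3.5-5.6 points | 1.9-3.3 points |
| 10 | 0.55-0.60 | 15-26% | 5.9-9.9 points | 3.1-5.4 points |

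**Does baseline pain already carry this?** A simulation of 2,000 trials per setting had baseline pain in the model and correlated with baseline rescue use (placebo rate 50%). Power without and with the rescue term was:
- n = 90: 57.2% and 57.5% (predictor OR 2), 47.7% and 52.0% (OR 5), 35.9% and 45.1% (OR 10).
- n = 43: 28.4% and 30.3%, 25.3% and 26.6%, 20.2% and 24.5%.
- No predictive value (OR 1): 61.5% and 61.2% at n = 90, and 32.9% and 33.4% at n = 43. With 2,000 trials the standard error is about √(0.6·0.4/2000) = 1.1 points, so neither is a real difference.
- No treatment effect: type I error was 4.9-5.2% with and without the term.

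**The case against.** Reusing the primary covariate set is a conventional prespecified choice, and nothing in the documents contradicts it. The endpoint is exploratory, with no power target and no decision rule. At 43 per arm the power in the formula calculations is only about 18-34% with or without the term. All of this stands, and it sets the weight of the point.

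It is also fair to say that the baseline record is not fully established. The Table 6-1 mark belongs to a combined row, the protocol's text on daily entries before randomization concerns pain scores, and SAP section 2.4.2.1 summarizes diary rescue only for the treatment and withdrawal periods. That is why the source and window have to be defined. The over-the-counter row of Table 5-2 raises a further question, but it covers the time before and after randomization alike. If it took in the rescue drug, it would conflict with section 5.5.6 throughout the study and not only at baseline.

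Sparse data are a real risk. Suppose 30% of 43 per arm use rescue at baseline, 95% of them use it later on placebo, and the treatment odds ratio is 0.4. There are then about 13 users per arm. The active proportion is 7.6/8.6 = 88%, and the expected non-events are 13·0.05 + 13·0.12, or about 2 in all. The new term could then separate.

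A reader might infer more than the documents support:
- **That earlier use is the strongest predictor.** No rescue rate or predictive strength is given. Large gains need strong assumptions. For example, later use of 80-95% in baseline users against 35-40% in others implies predictor odds ratios of 6 (4/0.667) to 35 (19/0.538).
- **That the planned odds ratio is biased.** The shift towards 1 is non-collapsibility.
- **That the Cox model needs the same change.** The current SAP no longer runs it.

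**Conclusion.** The point holds as a modest, optional gain in efficiency for one exploratory logistic model. The outcome's own baseline is missing from the covariate list although a record before randomization is scheduled. At the actual size of the trial the gain runs from negligible to about 5 points of power, depending on a predictive strength that the documents do not give. Validity is not in question, and neither the primary test nor the handling of pain scores under rescue is touched. The figures rest on the assumed treatment odds ratio, rescue rates and baseline prevalence set out above.

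**What to change.** In SAP section 2.13 (item 1), add rescue use for PHN pain in the 7 days before Visit 101 (yes/no) to the logistic model. Name the source (eDiary or eCRF) and define the window. State in advance that the current model is kept if recorded baseline use is too sparse or the term separates.

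Before the variable is derived, reconcile protocol section 5.5.6 with the over-the-counter row of Table 5-2 on whether the rescue drug falls under that row.

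Kaplan-Meier curves of first intake by baseline use are optional and descriptive only, since the groups would be small. No change to a Cox model is needed; SAP section 4 could list its removal.

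The cost is a sentence in the SAP, one derived variable and one model degree of freedom, settled before database lock. It depends on the rescue record before randomization being usable.
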